#### **2.4.3 Exploratory Endpoints**

- Relationship of XPO-1 expression to PSA decline.
- Expression profile of metastatic tumor and outcome.
- Type of progression (e.g. Pain, bone etc)
- Comparison of pre- and post-treatment XPO-1 expression in patients for whom pre-treatment biopsy is available through the Stand Up 2 Cancer "Dream Team" program.

### **3 Study Design**

#### **3.1 Characteristics**

Single agent phase II open label study of selinexor in patients with mCRPC with prior therapy with standard hormone ablation agents and abiraterone. We anticipate the involvement of at least 3-5 centers participating in the SU2C West Coast Dream Team (SU2C WCDT - UCSF, UCLA, UC Davis, Oregon Health Sciences University, University of British Columbia), as well as participating sites of the Prostate Cancer Clinical Trials Consortium. Pre therapy and end of therapy biopsies will be offered to patients at the SU2C WCDT centers only.

#### **3.2 Number of Subjects**

A maximum of 54 evaluable patients will be accrued for this study, provided the early stopping criteria are not met. The early stopping rules are described in the statistical section.

### 3.3 Eligibility Criteria

Patients must have baseline evaluations performed prior to the first dose of study drug and must meet all inclusion and exclusion criteria. In addition, the patient must be thoroughly informed about all aspects of the study, including the study visit schedule and required evaluations and all regulatory requirements for informed consent. The written informed consent must be obtained from the patient prior to enrollment. The following criteria apply to all patients enrolled onto the study unless otherwise specified.

#### 3.3.1 Inclusion Criteria

1. Age  $\geq$  18 years.
2. Histologically confirmed adenocarcinoma of the prostate.
3. Patients must have castrate levels of testosterone ( $< 50$  ng/dL) on GnRH analogues or have had prior orchiectomy. GnRH analogues must be continued while on study.
4. Tumor tissue submitted for molecular and genetic analysis through the companion SU2C radiologically guided biopsy of abiraterone and/or enzalutamide refractory mCRPC protocol.
  - a. Patients who consent to participate in the companion biopsy protocol and are subsequently determined to be ineligible for biopsy are eligible to participate in the current protocol.
5. Progressive disease as demonstrated by a rising PSA (at least two determinations) prior to study entry, and/or radiographic evidence of tumor progression in soft tissue according to modified RECIST criteria or identification of new lesions by bone scan (i.e.,  $\geq 2$  new lesions).
6. Primary resistance or acquired resistance (i.e., acquired resistance will be defined as disease progression following a period of response defined as  $\geq 50\%$  decline in PSA within 12 weeks of starting therapy and not otherwise meeting criteria for primary resistance) to any of the following agents/combinations of therapy:
  - a. Abiraterone acetate. Primary resistance to abiraterone will be defined as:
    - No PSA decline
    - PSA decline less than 50% after 12 weeks of abiraterone therapy
    - PSA progression within 12 weeks of AA treatment (by PCWG2 criteria), after initial response to therapy
    - Objective progression, by RECIST criteria for soft tissue lesions and by modified PCWG2 criteria for bone lesions within 12 weeks of starting abiraterone treatment
    - Unequivocal clinical progression (per the treating provider's discretion) within 12 weeks of starting abiraterone treatment
  - b. Enzalutamide. Primary resistance to enzalutamide will be defined as:
    - No PSA decline
    - PSA decline less than 50% after 12 weeks of enzalutamide therapy

- PSA progression within 12 weeks of enzalutamide treatment (by PCWG2 criteria), after initial response to therapy
  - Objective progression, by RECIST criteria for soft tissue lesions and by modified PCWG2 criteria for bone lesions within 12 weeks of starting enzalutamide treatment
  - Unequivocal clinical progression (per the treating provider's discretion) within 12 weeks of starting enzalutamide treatment
- c. Other second-generation investigational anti-androgen/androgen-receptor targeted therapies, including ARN-509. Primary resistance will be defined as:
- i. No PSA decline
  - ii. PSA decline less than 50% after 12 weeks of enzalutamide therapy
  - iii. PSA progression within 12 weeks of enzalutamide treatment (by PCWG2 criteria), after initial response to therapy
  - iv. Objective progression, by RECIST criteria for soft tissue lesions and by modified PCWG2 criteria for bone lesions within 12 weeks of starting enzalutamide treatment
  - v. Unequivocal clinical progression (per the treating provider's discretion) within 12 weeks of starting enzalutamide treatment
- d. Combination therapy with abiraterone, enzalutamide and/or other second-generation investigational anti-androgen/androgen-receptor targeted therapies, including ARN-509. Primary resistance to combination therapy will be defined as:
- No PSA decline
  - PSA decline less than 50% after 12 weeks of abiraterone and enzalutamide therapy
  - PSA progression within 12 weeks of abiraterone and enzalutamide treatment (by PCWG2 criteria), after initial response to therapy
  - Objective progression, by RECIST criteria for soft tissue lesions and by modified PCWG2 criteria for bone lesions within 12 weeks of starting abiraterone and enzalutamide treatment
  - Unequivocal clinical progression (per the treating provider's discretion) within 12 weeks of starting abiraterone and enzalutamide treatment
- e. Sequenced therapy, including any of the following:
- i. Abiraterone acetate followed by enzalutamide
    - 1. Primary resistance will be defined per criteria for abiraterone monotherapy primary resistance, section 3.3.1, item 5a
  - ii. Enzalutamide followed by abiraterone acetate
    - 1. Primary resistance will be defined per criteria for enzalutamide monotherapy primary resistance, section 3.3.1, item 5b
  - iii. Other second-generation investigational anti-androgen/androgen-receptor targeted therapies, including ARN-509.

1. Primary resistance will be defined per criteria for other investigational anti-androgen monotherapy primary resistance, section 3.3.1, item 5c
7. Presence of 1 or more bone metastasis.
8. ECOG Performance status 0 or 1.
9. Prior and ongoing zoledronic acid or denosumab therapy is allowed.
10. Prior therapy with radium-223 is allowed.
11. Discontinuation of prior therapy for mCRPC: A Washout period of 28 days for the following therapies is required: Abiraterone, enzalutamide, fluconazole, itraconazole, flutamide, bicalutamide, nilutamide, and other experimental hormonal agents (ARN509, TAK-700, etc.), sipuleucel-T (Provenge), other experimental vaccines (PROSTVAC-V/F, etc.), Strontium-89, Samarium, and Radium-223 chloride.
12. Baseline laboratory parameters:
  - Adequate bone marrow function:

Leukocytes	> 3,000/mcL
absolute neutrophil count	> 1,500/mcL
Platelets	> 125,000/mcL
Hemoglobin	≥ 5.59 mmol/L or 9 g/dL

Up to 5% deviation is tolerated. Transfusions and growth factors are allowed.
  - Adequate hepatic function:

Total bilirubin	within normal institutional limits
AST(SGOT)	< 3 X institutional upper limit of normal
ALT(SGPT)	< 3 X institutional upper limit of normal
  - Adequate renal function:

Creatinine	within normal institutional limits
OR	> 60 mL/min/1.73 m  for patients with creatinine levels above institutional normal
creatinine clearance	
13. Ability to understand a written informed consent document, and the willingness to sign it
14. Life expectancy of at least 12 weeks
15. Able to swallow and retain oral medication

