## 9.5 Registration/Enrollment

Screening procedures will occur when a subject and investigator signs and dates an informed consent form and the subject provides authorization to use protected health information. The informed consent form will be completed prior to any study-specific procedures. Screening procedures that are standard of care and were performed prior to consent, do not need to be repeated if they were conducted within the eligible screening period, unless otherwise specified.

To initiate enrollment, the investigator will verify eligibility according to all inclusion and exclusion criteria. All eligible subjects must be centrally registered through the GU Clinical Research Office. To complete the registration process, the study site must fax or email the signed completed study-specific eligibility checklist, all source documents verifying eligibility, any supporting documents, and the signed informed consent to the GU Clinical Research Office. These data must also be entered into the OnCore database. Once the enrollment packet is received at UCSF, the Study Chair will review the packet and if eligibility is confirmed, assignment to treatment can occur. Subjects failing to meet all study eligibility requirements will not be registered.

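### Inclusion items 6c and 6d judge resistance to other androgen-receptor agents by the response to enzalutamide, or to abiraterone plus enzalutamide, so a literal reading can refuse or mislabel some patients

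*Combined protocol and SAP*

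**What the plan says.** Section 3.3.1, item 6, asks for primary or acquired resistance to any one of five listed kinds of prior therapy (6a to 6e). Acquired resistance means progression after a PSA fall of at least 50% within 12 weeks of starting therapy, in a patient "not otherwise meeting criteria for primary resistance".

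- **6a and 6b** each give five primary-resistance criteria. The first, no PSA decline, names no drug. The other four name the drug that the item covers. In 6a the second criterion is "PSA decline less than 50% after 12 weeks of abiraterone therapy"; 6b has the same wording for enzalutamide.
- **6c** covers other second-generation androgen-receptor agents, ARN-509 among them. Its criterion ii is "PSA decline less than 50% after 12 weeks of enzalutamide therapy", and criteria iii to v also refer to enzalutamide.
- **6d** covers combinations of abiraterone, enzalutamide and/or those other agents. Its second criterion is "PSA decline less than 50% after 12 weeks of abiraterone and enzalutamide therapy", and the three after it name the same pair.
- **6e** covers sequenced therapy and points elsewhere for its definitions. Its first line reads "Primary resistance will be defined per criteria for abiraterone monotherapy primary resistance, section 3.3.1, item 5a"; the next two cite items 5b and 5c. Item 5 begins "Progressive disease as demonstrated by a rising PSA (at least two determinations) prior to study entry" and has no sub-items.

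Section 3.3 makes every inclusion criterion mandatory. Section 9.5 adds: "Subjects failing to meet all study eligibility requirements will not be registered".

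**The concern.** Item 6c exists to admit patients whose qualifying drug is neither abiraterone nor enzalutamide. The protocol expects such patients, since the washout list in item 11 names ARN509 and TAK-700. Yet four of the five 6c criteria ask about a drug that these patients may never have taken. The wording appears to have been carried over from 6b without changing the drug name, and 6d has a similar fault.

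Item 6 has two uses: it decides entry, and it is the only place that defines primary and acquired resistance. A fault here can therefore turn away a patient the protocol meant to include, or give an enrolled patient a class different from the one he would receive under 6a or 6b for the same course.

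**Working it through.** **Design figures.** The point has no figure of its own in the plan, so the only check to make is whether it touches the two-stage design in section 8.2.1. Inputs: 18 patients in stage 1, stop if 10 or fewer are progression-free; 54 in total, reject if 36 or more are; p0 = 0.55, p1 = 0.75.

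- Early stopping: sum over x = 0 to 10 of C(18,x) p^x (1−p)^(18−x). At p = 0.55 this is 0.6085 (stated 60.9%).
- Rejection: sum over x = 11 to 18 of P(X1 = x) × P(X2 ≥ 36 − x), with X2 binomial on 36 patients. At 0.55 this is 0.0477 (stated 0.048); at 0.75 it is 0.9007 (stated 90.0%).

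The design reproduces, and resistance class enters none of these formulas.

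**Item 6c applied to a patient treated only with a 6c agent.** He has had no enzalutamide, so criteria ii to v cannot be met as written. That leaves criterion i and the definition of acquired resistance. The last column applies the pattern of 6a and 6b, in which the named drug is the one received.

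| PSA course on the 6c agent | 6c read literally | Pattern of 6a/6b |
|---|---|---|
| No decline | Primary (criterion i) | Primary |
| Decline above 0 but below 50% at 12 weeks, then progression | Neither, so item 6 fails | Primary |
| Decline of at least 50%, progression within 12 weeks | Acquired | Primary |
| Decline of at least 50%, later progression | Acquired | Acquired |

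Two of the four courses go wrong. In the second row criterion i fails because there was a decline, and acquired resistance fails because the decline did not reach 50%. In the third row the patient stays eligible and only his label changes.

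**Item 6d.** Take abiraterone plus ARN-509 with a 30% PSA decline. He had no enzalutamide, so the four criteria that name both drugs are not met as written, and the second row applies again. He may still enter through 6a, whose wording does not say that abiraterone must have been given alone; on the other side, 6e describes the 6a criteria as monotherapy criteria. The text does not settle which applies. A combination of two other agents, with neither named drug, has no such route. A triple combination that contains both named drugs meets the 6d wording.

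**Item 6e.** Lines i and ii cite 5a and 5b but also say in words that the abiraterone and enzalutamide monotherapy criteria are meant, which are 6a and 6b. Line iii points in the same way to the criteria for other agents, which are 6c, and so takes over the fault in 6c.

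**The case against.** The strongest reply is that the intent is plain. Items 6a and 6b set the pattern, and anyone familiar with the protocol would read the drug named in 6c as the drug received. Registration is also central: under section 9.5 the Study Chair reviews each packet and its source documents before treatment is assigned. A reader might infer that sites will register patients whom other sites turn away. Central review largely prevents that, although local pre-screening could still differ. What stands is that no other section corrects the wording, and a mandatory criterion should not depend on the reviewer setting its text aside.

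Three further inferences are tempting and are not supported:

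- **Dilution of the primary-versus-acquired comparison.** Section 8.4.3 compares rPFS by *abiraterone* resistance. A patient given only ARN-509 has no abiraterone-resistance status, and cohorts A to D in section 8.4.1 have no place for him. Nor do the documents say that acquired resistance carries the better prognosis: section 1.1 gives a single survival figure after progression, about 19 months, for both types. What remains is possible misclassification of patients given abiraterone together with another agent.
- **A count of affected patients.** The documents give no share for 6c or 6d patients. The title, item 4 and sections 3.1 and 8.1.1 centre on abiraterone and/or enzalutamide, so there may be very few. Anyone refused entry would not be among the 54.
- **Harm from the 5a to 5c references.** These are a numbering slip. Because 6e names its targets in words, the slip alone need not misclassify anyone.

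**Conclusion.** Wrong as written; minor severity. For a patient treated only with a 6c agent, four of the five primary-resistance criteria cannot be met on their literal terms, and two of four PSA courses give a result different from the 6a/6b pattern: one can lead to refusal, the other changes the class only. The same can occur under 6d for combinations that lack one or both named drugs, unless the patient is classified through 6a or 6b. Item 6e(iii) inherits the 6c fault.

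This rests on a literal reading and on the assumption that 6c and 6d were meant to follow 6a and 6b. It does not show that patients are in fact being excluded, only that they can be if the text is applied as it stands. The number affected is unknown, the effect on the abiraterone-resistance comparison is limited, and the stated type I error and power do not change.

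**What to change.** In 6c, criteria ii to v, replace enzalutamide with *the qualifying agent*. In 6d, replace the named pair in the last four criteria with *the combination received*. In 6e, change 5a, 5b and 5c to 6a, 6b and 6c. Add two fields to the eligibility checklist: the qualifying agent or combination, and the resistance criterion met.

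The cost is a wording amendment through the approvals in section 9.4 and a checklist update. It needs no extra procedures or patients, and no change to the design.

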### 3.3.2 Exclusion Criteria

1. Untreated brain metastases. Brain metastases ≤1 cm and not associated with any focal neurologic deficits are allowed.

2. Prior docetaxel or other chemotherapy for mCRPC. Patients who have received docetaxel for metastatic hormone-sensitive prostate cancer are eligible.
3. Active or symptomatic viral hepatitis or chronic liver disease
4. Clinically significant heart disease as evidenced by myocardial infarction, or arterial thrombotic events in the past 6 months, severe or unstable angina, or New York Heart Association (NYHA) Class II-IV heart disease or known cardiac ejection fraction measurement of <50 % at baseline.
5. Patients with significantly diseased or obstructed gastrointestinal tract or uncontrolled vomiting or diarrhea or other gastrointestinal disorders (medical disorders or extensive surgery) that may interfere with the absorption of the study agents
6. Pure small cell carcinoma of the prostate or any mixed histology cancer of the prostate (eg: neuroendocrine) that contains <50% adenocarcinoma, as observed on biopsy obtained at the time of diagnosis or on any subsequent biopsies. Any "currently active" second malignancy, other than non-melanoma skin cancer. Patients are not considered to have a "currently active" malignancy, if they have completed therapy and are considered by their physician to be at least less than 30% risk of relapse over next year.
7. Any condition, which in the opinion of the investigator, would preclude participation in this trial.
8. Active psychiatric illnesses/social situations that would limit compliance with protocol requirements.
9. Patients in whom urgent treatment with docetaxel is indicated, per clinician discretion. This includes, but is not limited to patients with symptomatic visceral metastatic disease
10. Uncontrolled infection or concomitant medical illness that is not adequately controlled with current medical management, as determined per clinician discretion.
11. Active bleeding disorders or evidence of evidence of chronic or acute disseminated intravascular coagulation (DIC)
12. Severely compromised immunological state, including known human immunodeficiency virus (HIV)
13. Any acute toxicities due to prior anti-cancer treatments and/or radiotherapy that have not resolved to a NCI CTCAE Grade of  $\leq 1$  (except alopecia)
14. Prior radiation therapy completed <3 weeks or single fraction of palliative radiotherapy <14 days prior to first dose of KPT-330
15. Initiation of bisphosphonate therapy <4 weeks prior to first dose of KPT-330. Patients receiving bisphosphonate or denosumab therapy must be on stable doses for at least 4 weeks prior to first dose of KPT-330.
16. Men unable or unwilling to employ 2 forms of highly effective contraception throughout the study and for 8 weeks after the end of study treatment

### 3.4 Duration of Therapy

In the absence of treatment delays due to adverse events, treatment may continue until:

- Disease progression
- Inter-current illness that prevents further administration of treatment
- Unacceptable adverse event(s), including any occurrence of grade 4 neurotoxicity
- Patients decides to withdraw from the study
- Significant patient non-compliance with protocol
- General or specific changes in the patients' condition render the patient unacceptable for further treatment in the judgment of the investigator.

### 3.5 Duration of Follow Up

Patients will be followed for 30 days after completion of treatment or removal from study, or until death, whichever occurs first. Patients removed from study for unacceptable treatment related adverse event(s) will be followed until resolution or stabilization of all treatment related adverse events to Grade 2 or lower.

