### 6.1.3 End-of-Treatment Study Procedures

- To be completed within 30 days of the last dose of study drug.
- Physical examination
- Vital signs
- Performance Status
- Evaluation of adverse events
- Concomitant medications
- Brief Pain Inventory (BPI) short form
- Tumor biopsy -- optional, per companion Radiologically Guided Biopsy protocol of mCRPC, offered to patients treated at UCSF, UCLA, UC Davis, Oregon Health Sciences University, University of British Columbia
- Ophthalmologic exam including slit lamp examination and visual acuity prior to dilation, and a dilated fundoscopic evaluation and slit lamp examination.
- Laboratory evaluations
  - CBC with differential and platelet count
  - Blood chemistry assessment
  - PSA

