#### **6.1.4 End-of-treatment long-term follow-up**

- To be completed at 6 month intervals after the last dose of study drug.
- Telephone visit for assessment of adverse events, concomitant medications and subsequent antitumor therapy.

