**Table 6.1 Schedule of Study Procedures and Assessments**

Visits must occur ±7 days of planned visit unless otherwise noted.

Period/ Procedure	Screening				Cycle 1		Cycle 2 and future Cycles	End of Treatment visit	Follow- up visits
	-28 to 0	1	3 	15	1	1	Within 30 days of last dose	By phone Every 6 months	
Treated leukocyte lysate 		X							
Serum MIC-1 mRNA 		X		X	X				
Selinexor PK 		X							
Testosterone	X								
Imaging procedures									
CT c/a/p with contrast or MRI	X					X 			
ECG/EKG	X								
Bone scan (Technetium)	X					X 			

 Required at screening and as clinically indicated while on study. Coagulation labs include PT, PTT/INR.

 Only offered to patients at UCSF, UCLA, UC Davis, Oregon Health Sciences University, University of British Columbia. If no intervening therapy is initiated, the tumor biopsy can be performed within a 2-month window (60 days) of day 1 of Selinexor.

 Including alkaline phosphatase, ALT/AST, total bilirubin, calcium, phosphorus, (BUN), creatinine, total protein, albumin, fasting glucose, potassium, sodium, chloride, bicarbonate, uric acid, LDH, fasting lipid panel (LDL, total cholesterol, triglycerides).

 Monthly and at time of progression

 Only Cycle 2 and Cycle 4, Day 22-28, and at time of progression

 PK samples will be collected on Cycle 1 Day 1 only. PD Samples will be collected on Cycle 1 Day 1 and 15, Cycle 2 Day 1, and cycle 3 Day 1. Refer to section 6.3 for PK and PD collection schedule.

 At the completion of Cycle 2, Cycle 4, Cycle 6, Day 22-28, and every 12 weeks thereafter

 Required at screening, every 3 months thereafter if cataracts identified at screening and if clinically indicated, and at the end of treatment study visit.

 C1D3 visit will be conducted via telephone call

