#### **8.4.2 Primary Analysis (or Analysis of Primary Endpoints)**

The primary end point is proportion of patients without evidence of radiographic progression at 16 weeks. This is defined from study start until one of the following events occurs:

- $\geq 2$  new bone lesions on Technetium bone scan
- RECIST defined tumor progression
- Cancer related pain requiring opiate analgesics
- Surgery or Radiation to treat a prostate cancer related indication
- Death from any cause

Radiographic PFS will be defined as the time from treatment initiation to the occurrence of either tumor progression in soft tissue according to modified RECIST criteria, identification of new lesions by bone scan ( $\geq 2$  new lesions confirmed  $\geq 12$  weeks later). If no such event exists, then rPFS will be defined as time from start of study until clinical deterioration requiring a change in prostate cancer therapy or at clinician discretion, surgery and/or radiation therapy to treat a prostate-cancer related indication, or death from any cause. PFS will be censored at the last scheduled disease assessment on study. PFS of living patients with no assessment on-study, and PFS of patients with no baseline assessment will be censored at enrollment.

rPFS will be estimated using the Kaplan-Meier product limit method. The median times to event with two-sided 95% confidence intervals will be estimated, together with the estimate of event rates at 6 and 12 months. The score statistic from the cox proportional hazards model will be used in the estimation of the hazard ratio and the associated 95% confidence interval will also be provided.

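### The follow-up rules conflict (30 days in 3.5, six-monthly calls in 6.1.4) and neither collects radiographic progression or vital status after a stop without progression, so the Kaplan-Meier rPFS estimates may be biased

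*Combined protocol and SAP*

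**What the plan says.** **Length of follow-up.** Section 3.5 and the abstract: "Patients will be followed for 30 days after completion of treatment or removal from study, or until death, whichever occurs first". The next sentence extends this only for patients removed for treatment-related adverse events. Section 6.1.4 sets a different schedule, "To be completed at 6 month intervals after the last dose of study drug", with no stated end. Table 6.1 repeats the six-monthly telephone visit.

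**Content of follow-up.** The end-of-treatment visit in 6.1.3 is "To be completed within 30 days of the last dose of study drug". It lists examination, laboratory tests, PSA, pain inventory, eye examination and an optional biopsy, but no CT, MRI or bone scan. The call in 6.1.4 is a "Telephone visit for assessment of adverse events, concomitant medications and subsequent antitumor therapy"; progression and vital status are not listed. Imaging is scheduled by cycle (Table 6.1, footnote 7): "At the completion of Cycle 2, Cycle 4, Cycle 6, Day 22-28, and every 12 weeks thereafter".

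**Analysis.** Section 8.4.2 counts soft-tissue and bone progression, clinical deterioration leading to a change of therapy, surgery or radiation, and death from any cause as rPFS events. On censoring it says "PFS will be censored at the last scheduled disease assessment on study" and "PFS of living patients with no assessment on-study, and PFS of patients with no baseline assessment will be censored at enrollment". It plans Kaplan-Meier medians "together with the estimate of event rates at 6 and 12 months".

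**The concern.** The two follow-up rules cannot both govern. A site working from 3.5 would never make the calls in 6.1.4.

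The larger issue is what is collected. Section 3.4 lists several reasons for stopping other than progression: adverse events, intercurrent illness, withdrawal, non-compliance. After such a stop the patient remains at risk of the events that define rPFS, but no procedure looks for radiographic progression or records survival status. Section 8.4.2 then censors the patient. Kaplan-Meier treats censored patients as having the same future risk as those still on drug. If those who stop do worse, the curve is too favourable; if they do better, it is too unfavourable. Dates that were never collected cannot be recovered at the analysis stage.

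**Working it through.** **1. The plan's own figures.** The inputs below come from the design in 8.2.1, so I checked it first. With 18 patients in stage 1 (stop at 10 or fewer) and 36 or more of 54 needed:
- P(X1 ≤ 10 | 18, 0.55) = 0.6085 (stated 60.9%).
- Rejection probability, summing P(X1 = x)·P(X2 ≥ 36 − x | 36, p) over x = 11 to 18: 0.0477 at p = 0.55 (stated 0.048) and 0.9007 at p = 0.75 (stated 90.0%).

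The design reproduces, and this point does not alter it.

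**2. One patient followed through the text.** Suppose a patient stops at week 6 without progression.
- Section 3.5 ends follow-up 30 days later, at about week 10, unless a treatment-related adverse event is still being followed.
- The first scan falls at the end of Cycle 2 (week 8), so it is not reached. If disease assessment means imaging, 8.4.2 censors this living patient at enrollment, and he contributes nothing to the curve.
- Under 6.1.4 the first call falls at week 6 + 26 = 32 and the second at week 58. Both come after the landmark they would inform (weeks 26 and 52).

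**3. Possible size.** Section 8.2.1 gives 55% and 75% progression-free at 16 weeks. The documents give no discontinuation rate and no off-drug hazard, so the following are assumptions:
- Constant on-drug hazard at the alternative: l1 = −ln(0.75)/16 = 0.01798 per week.
- Constant off-drug hazard at the null: l0 = −ln(0.55)/16 = 0.03736 per week, 2.08 times l1.
- Constant stopping rate without progression: s = −ln(1 − q)/16, where q is the proportion stopping by week 16 in the absence of progression. For q = 15%, 25% and 35%, s = 0.01016, 0.01798 and 0.02692.

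Kaplan-Meier censored at stopping estimates exp(−l1·t). Complete follow-up gives

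S(t) = exp(−(l1+s)t) + s·[exp(−l0·t) − exp(−(l1+s)t)] / (l1 + s − l0).

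For q = 25%: at t = 26, 0.3926 + 0.1802 = 0.573; at t = 52, 0.1541 + 0.1390 = 0.293.

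| Stopping by week 16 | 6 months: KM / complete | 12 months: KM / complete |
|---|---|---|
| 15% | 62.7% / 59.4% | 39.3% / 32.9% |
| 25% | 62.7% / 57.3% | 39.3% / 29.3% |
| 35% | 62.7% / 55.2% | 39.3% / 26.3% |

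The gaps are 3.3 to 7.5 points at 6 months and 6.4 to 13.0 points at 12 months.

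**4. Dependence on the hazard ratio.** If l0 = l1, the formula collapses to exp(−l1·t) and the gap is zero for any q. If l0 = l1/2 with q = 25%, complete follow-up gives 65.9% and 46.9%, so Kaplan-Meier is too low.

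**5. A second parameterisation.** Here the overall 16-week rate is fixed at 55% or 75%, 10-30% stop by week 16, and the off-drug hazard is 1.5 to 3 times the on-drug hazard. Kaplan-Meier overstates the progression-free proportion by 1-11 points at week 26 and 2-18 points at week 52.

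**6. The written censoring rule.** Step 3 censors at the stop date, whereas 8.4.2 censors at the last scan. A simulation used scans at weeks 8, 16, 24, 36, 48 and later, censoring at the last scan or at time zero if there was none. With 75% on-drug at week 16, 20% stopping and a hazard ratio of 2, the planned estimate was 0.649 against 0.613 with complete follow-up at week 26, and 0.421 against 0.347 at week 52. About 11% of patients were censored at time zero. With a ratio of 1 the two estimates agreed to within 0.001.

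**The case against.** **Direction.** A reader might infer that the planned 6- and 12-month rates are simply too high. The documents do not support that. Section 8.4.2 plans event rates, which would be too low under the model in step 3. Any bias also requires a higher hazard after stopping, which no section establishes. Setting off-drug risk at the null and on-drug risk at the alternative presumes that the drug works; if it does nothing, the two hazards coincide and this source of bias disappears. This objection stands, and the conclusion is conditional for that reason.

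**How much is lost.** A reader might also infer that rPFS after stopping is wholly unobserved. That is too strong. The calls ask about later antitumor therapy, which bears on the therapy-change component. They ask about adverse events, and a fatal one is Grade 5 (7.6). Deaths within 30 days fall inside 3.5. Patients removed for toxicity are followed longer under 3.5 and the notes to Table 5.3, although for the adverse event and not for progression. What is lost is mainly radiographic progression and a dated vital status. The plan does not say whether information from a call counts as an rPFS event.

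**Extrapolation.** A constant rate with 25% stopping by week 16 implies 1 − 0.75^(52/16) = 61% stopping by week 52 in the absence of progression, or 0.5 × (1 − 0.1541) = 42% allowing for competing progression. The 12-month figures therefore rest on a strong assumption and are illustrative only.

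**Importance.** The stated objective is descriptive, and the go/no-go decision uses the 16-week proportion, not the Kaplan-Meier rates. This is fair and limits the weight of the point. How a patient who stops unscanned before week 16 is classified in the 18/54 rule is a related but separate question that section 8 also leaves open.

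**Reading of the table.** The imaging rows of Table 6.1 are damaged in the text available for this review, so the absence of an end-of-treatment scan rests on the 6.1.3 list and footnote 7.

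**Conclusion.** The point holds in conditional form. Two follow-up rules conflict, and neither systematically captures radiographic progression or vital status after a stop without progression, although both are rPFS events in 8.4.2. The resulting censoring may be informative.

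Under the assumptions in step 3 the progression-free proportion is overstated by about 3 to 8 points at 6 months and 6 to 13 points at 12 months, and event rates are understated by the same amounts. The stopping rate, the off-drug hazard and the constancy of both are assumptions. The direction depends entirely on whether risk is higher, equal or lower after stopping. The change is worth making because it is cheap now and the missing dates cannot be recovered later.

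**What to change.** 1. Reconcile 3.5, the abstract, 6.1.4 and Table 6.1 so that one follow-up rule applies.
2. For patients who stop without an rPFS event, add date and type of progression (from routine-care scans) and vital status with date of death to the calls. Add one contact around week 16, and continue until an event or 12 months from treatment start.
3. State in 8.4.2 that these reports count as rPFS events, and whether later therapy reported on a call counts.
4. Report the analysis censored at discontinuation as a sensitivity analysis, with the number of patients censored for stopping without progression and the number censored at enrollment.

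**Cost.** Protocol wording, a few CRF fields and one extra call for patients who stop early. Sample size and the two-stage rule are unchanged. At 5 patients per month, 54 / 5 = 10.8 months of accrual plus 12 months of follow-up is about 23 months, within the 36-month data-collection window in 3.6.2.

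**Limits.** Routine-care scans will be irregularly timed and may follow new therapy, and patients who withdraw may decline contact. The calls reduce the gap but cannot fully replace scheduled imaging.
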